#### Depression

**Trends in endpoints.** In addition to the primary and secondary endpoints described above, we will compare the time trends in the endpoint depression symptom scores at baseline, 1, 3, and 6 months among the CYP2D6 PM or UM or CYP2C19 UM, RM or PM subgroup, using a repeated-measures mixed effect model. Since participants are randomized to Intervention and Control groups and not to the CYP2D6 PM or UM or CYP2C19 UM, RM or PM subgroup within Intervention and Control groups, there could be important differences in baseline characteristics between the two groups. For these

reasons, we will conduct covariate-adjusted repeated measures mixed models that will account for differences in baseline characteristics that differ between the Intervention – CYP2D6 PM or UM or CYP2C19 UM, RM or PM subgroup and the Control – CYP2D6 PM or UM or CYP2C19 UM, RM or PM subgroup. Potential baseline characteristics may include age, sex, income, education, insurance, medical conditions. We will select the appropriate covariance matrix (e.g. compound symmetry, autoregressive, unstructured, or other covariance structure) based on the data.

*Difference within the NM group.* In the control arm participants, we will compare depression scores and depression control in participants with a CYP2D6 activity score  $>0.75 - 1$  to participants with an activity scores  $>1-2$  using a two-sided two-sample t-test or Mann Whitney test, as appropriate, with a type 1 error of 0.05. Additionally, we will use linear regression to adjust for differences in baseline characteristics

#### Cost Effectiveness

*Healthcare costs:* In the Medicare fee-for-service or Medicaid enrollees, log-transformed overall expenditures (between index visit and 6 months follow-up) will be compared using a 2-sample t-test between the study arms (after ensuring that the variances in the log-scale are equal). Alternatively, cost comparisons will be made using appropriate regression models such as generalized linear models. For all participants, regardless of insurance type, we will estimate and aggregate participant-reported healthcare utilization during follow-up and assign cost for each item based on unit weighted mean cost estimates from the Medicare/ Medicaid data.

Within the Medicare/Medicaid population, we will compare estimated cost differences between genotype-guided and usual care based on billing records versus participant report to further validate the cost comparisons for the entire population. Cost for the index hospitalization for surgery participants will not be included in the cost estimate, but we will compare length of stay between groups as reference for hospitals regarding potential cost savings in capitation-based reimbursement schemes. All costs will be converted to 2021 \$US using the chain-weighted Consumer Price Index (CPI).

Finally, we will compare the Medicare/Medicaid beneficiaries among our trial enrollees to a larger random sample of beneficiaries in the participating states and compare demographic and key clinical characteristics to explore representativeness of our study sample, evaluate the impact of attrition and loss to follow-up and make inferences about the generalizability of our results.

*Cost utility:* For the cost-utility analysis, the PROMIS-43 responses will be converted into utilities using previously validated crosswalks.[41] Cost and quality adjusted life year (QALY) estimates, adjusted for clustering within site and baseline utility for QALYs, will be obtained using appropriate regression models such as generalized linear models. The analysis of maximum likelihood parameter estimates will allow us to capture differences in cost and QALYs between the intervention arm and control arm of the trial. The Incremental cost-effectiveness ratio (ICER) will be calculated from costs and QALY. A bootstrapping approach will be used to characterize sampling uncertainty and calculate confidence intervals (CI) around the ICER estimate (2.5th and 97.5th percentiles corresponding to the lower and upper bounds of the CI, respectively). This sampling uncertainty will be summarized using cost-effectiveness acceptability curves.

Details of these statistical analyses, along with other exploratory analyses will be described in the study SAP.

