#### **4.1 Randomization**

After participants provide informed consent/assent, participants will be randomized in a 1:1 allocation to the Intervention (i.e. immediate PGx testing and genotype-guided opioid or SSRI therapy with clinical decision support) and Control (i.e. usual care with delayed PGx testing) arms. Randomization will be stratified by trial and site or clinic with a random block size within each site or clinic. We anticipate variability in patient populations between recruiting sites or clinics and aim to balance the intervention assignments within the site or clinic unit. Additionally, the randomization for the chronic pain trial will be stratified by presence/absence of depression, and the randomization for the acute pain and depression trials will be stratified by pediatric/adult.

The randomization scheme will be generated by an unblinded statistician. Randomization assignments will be generated in real time in REDCap at the Coordinating Center.

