## 9. MEDICARE AND MEDICAID CLAIMS DATA COLLECTION AND ANALYSIS

### 9.1 Rationale

The economic analyses will be conducted from the perspective of the payer with the primary goal to provide cost-effectiveness data that can inform reimbursement decisions for genotyping. Reporting metrics will include:

1. Average costs for each study arm, considering overall cost to the payer and select services directly relevant to the acute pain, chronic pain, and depression groups
2. Differences in cost utility between the intervention arm, considering overall cost to the payer and select services directly relevant to the acute pain, chronic pain, and depression groups
3. Incremental cost-effectiveness ratio (ICER), i.e., the incremental change in cost per unit improvement of effectiveness.

All metrics will be ascertained over a 6-month follow-up period with the assumption that beneficial effects of genotype-guided therapy are fully realized within this time period and that the control arm participants have not yet developed any cross-over effects from the 6-month delayed testing.

In a population of mixed payer types, collecting actual costs for all participants is not feasible. Therefore, costs will be obtained from Medicare and Medicaid claims data and imputed or cross-walked to the other payer types. Based on data in the National Inpatient Sample, 53% and 4% of knee and 59% and 4% of hip arthroplasties were reimbursed by Medicare and Medicaid, respectively. For chronic pain participants, data from the University of Florida suggest 40% and 20% are covered by Medicare and Medicaid, respectively. Thus, considering enrollment gaps, at least 60% of the study population is anticipated to have claims data, from which comprehensive cost analyses can be performed and extrapolated to the entire cohort. Major cost drivers associated with pain and depression will be ascertained from the participant using validated resource questionnaires, and verified through secondary claims data whenever possible.

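### The planned percentile bootstrap interval for the ICER cannot be interpreted if replicates straddle a zero QALY difference; net monetary benefit from the same replicates avoids this

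*Combined protocol and SAP*

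**What the plan says.** The cost-utility paragraph under Cost Effectiveness in section 10.6 sets out these steps:

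- Utilities: "the PROMIS-43 responses will be converted into utilities using previously validated crosswalks".
- Adjustment: cost and QALY estimates come from regression models, "adjusted for clustering within site and baseline utility for QALYs".
- Ratio: "The Incremental cost-effectiveness ratio (ICER) will be calculated from costs and QALY".
- Uncertainty: a bootstrap is used to "calculate confidence intervals (CI) around the ICER estimate", with the 2.5th and 97.5th "percentiles corresponding to the lower and upper bounds of the CI, respectively".
- Second summary: "This sampling uncertainty will be summarized using cost-effectiveness acceptability curves".

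Section 9.1 fixes the horizon: "All metrics will be ascertained over a 6-month follow-up period". It also gives the purpose, which is to inform payers' reimbursement decisions.

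The combined document gives no expected QALY difference, utility SD, cost difference, cost SD or willingness-to-pay value. It has no rule for replicates in different quadrants of the cost-effectiveness plane, and it mentions neither net monetary benefit nor a Fieller interval. Further detail is left to a separate SAP.

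**The concern.** Taking percentiles of bootstrapped ratios assumes that sorting the ratios sorts value for money. That holds while every replicate has a QALY difference of the same sign. It fails when some replicates are positive and some negative, because the meaning of a low ratio then reverses partway through the list.

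A payer would read the resulting interval as a range of plausible costs per QALY, and it would not be one. It is always finite, so it gives no sign that the data are compatible with no QALY difference, where the ratio does not exist. Section 9.1 says these results are meant for reimbursement decisions, so a summary that cannot be read is a weakness even though no efficacy conclusion depends on it.

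**Working it through.** **Starting point.** The plan states no figure on this point, so there is none to reproduce. From the documents I use the method, the 6-month horizon, 1:1 allocation ("participants will be randomized in a 1:1 allocation"), and the completers per arm in section 10.1: 845 (acute pain), 447 (chronic pain) and 678 (depression), with 152, 134 and 271 per arm in the actionable subsets. The cost-utility paragraph does not say which population it uses. Everything else below is assumed.

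**Why the ordering fails.** Let dC and dQ be the differences in cost and QALYs, R = dC/dQ, and NMB = λ·dQ − dC = dQ·(λ − R) at willingness to pay λ.

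- If dQ > 0, NMB is positive when R < λ, so a lower ratio is favourable.
- If dQ < 0, NMB is positive when R > λ, so a higher ratio is favourable.
- Replacing (dC, dQ) by (−dC, −dQ) leaves R unchanged and reverses the sign of NMB.

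A change in the sign of dC alone does no such harm. What matters is whether dQ straddles zero.

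**How near zero is plausible?** SE(dQ) = 0.5 × SD × √(2/n), and dQ = 0.5 × utility gain. The 0.5 cancels in dQ/SE, so a short horizon does not by itself bring the difference nearer zero in SE units; the size of the gain relative to its SE does. For assumed gains of 0.005 to 0.03 and SDs of 0.10 to 0.20:

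| Trial | All completers, dQ/SE | Actionable subset, dQ/SE |
|---|---|---|
| Acute pain | 0.51 to 6.2 | 0.22 to 2.6 |
| Chronic pain | 0.37 to 4.5 | 0.20 to 2.5 |
| Depression | 0.46 to 5.5 | 0.29 to 3.5 |

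The top of each range is a gain of 0.03 with SD 0.10.

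**How often would a trial straddle zero?** The chance that the 95% interval for dQ includes zero is Φ(1.96 − z) − Φ(−1.96 − z), where z is the true dQ in SEs. This gives 83% at z = 1, 48% at z = 2 and 2% at z = 4. In those trials the Fieller set is unbounded, while the percentile interval stays finite.

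**Worked example** (678 per arm; assumed utility SD 0.15, cost SD $8,000, extra cost $300, λ = $50,000, no correlation between cost and QALYs). √(2/678) = 0.0543, so SE(dQ) = 0.075 × 0.0543 = 0.00407 and SE(dC) = 8,000 × 0.0543 = $434.

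| | Gain 0.01 | Gain 0.02 |
|---|---|---|
| dQ | 0.005 (1.23 SE) | 0.010 (2.45 SE) |
| True ICER | 300/0.005 = $60,000 | 300/0.010 = $30,000 |
| Replicates with dQ < 0 | 11% | 0.7% |
| 95% interval for dQ (± 1.96 SE) | −0.003 to 0.013 | 0.002 to 0.018 |
| Percentile ICER interval | about −$708,000 to +$859,000 | about −$78,000 to +$210,000 |
| ICER coverage (nominal 95%) | 98 to 99% | 97 to 98% |
| NMB coverage | about 95% | about 95% |

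For the 0.01 gain, mean NMB is 50,000 × 0.005 − 300 = −$50. Its SE is √((50,000 × 0.00407)² + 434²) ≈ $480, so the interval is −$991 to $890. Reflecting every replicate through the origin gives −$890 to $991 for NMB and exactly the same ICER interval.

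**Coverage against distance from zero** (simulation in SE units; cost difference 2 SE, correlation −0.3 to 0.3):

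| True dQ | Percentile ICER coverage |
|---|---|
| 0.1 SE | about 54% |
| 0.25 SE | 88 to 89% |
| 0.5 SE | 94 to 95% |
| 1 to 3 SE | 96 to 98% |
| 4 SE | 95 to 96% |

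With a cost difference of 0.5 SE the pattern is milder: 88% at 0.1 SE, 96% at 0.25 SE, 96 to 99% from 0.5 to 3 SE, and 94% at 4 SE. NMB coverage was about 94 to 96% throughout, including at a true QALY difference of zero, where the ICER does not exist.

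**The case against.** Much of the case on the other side stands.

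- **The condition is not shown.** Straddling rests on assumed gains and SDs. A reader might infer that the interval will fail in these trials; the documents do not support that. At about 4 SE or more from zero it behaves acceptably.
- **Baseline adjustment helps.** The plan adjusts QALYs for baseline utility, and the example above does not. With an assumed baseline correlation of 0.6 to 0.7 the SE shrinks by √(1 − r²) = 0.80 to 0.71. At a gain of 0.01, negative replicates fall from 11% to about 6 to 4%; at 0.02 they fall to about 0.1% or less. An analysis of the smaller actionable subset would push the other way.
- **Coverage is mostly conservative.** A reader might infer false precision. Over most of the range the interval is too wide; it under-covers only very close to zero. The main charge is that it cannot be interpreted.
- **The 0.02 example is weak evidence of mixing.** Only 0.7% of its replicates have a negative QALY difference, while about 24% are cheaper and better. Its negative lower bound mostly reflects real cost uncertainty.
- **Acceptability curves are planned.** At each threshold the curve is the share of replicates with positive net benefit, so a reader who infers that the plan lacks a decision summary would be wrong. The stated ICER interval would still appear beside the curve.
- **Detail is deferred to a separate SAP.** A quadrant rule could be there. But the percentile method is already stated, so this is a commitment to correct rather than a detail left open.

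**Conclusion.** The point holds conditionally. If the replicates straddle a zero QALY difference, the planned ICER interval mixes quadrants and cannot be interpreted. That is plausible for utility gains of roughly 0.005 to 0.02, but the gain and the SD are both assumptions.

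It would also go too far to conclude that an ICER interval needs every replicate in one quadrant. The ordering breaks on the sign of the QALY difference, not of the cost difference. In simulations with the QALY difference 4 to 6 SE from zero and the cost difference about 0.7 SE, percentile coverage was 94 to 95%, yet under 1% of trials had all 2,000 replicates in one quadrant.

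The synopsis calls the cost-effectiveness analyses exploratory. No primary or secondary conclusion, sample size or safety decision depends on this, so it is an inexpensive improvement and not a flaw in the trials' main inference.

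**What to change.** In the cost-utility paragraph and the separate SAP, report the following from the same bootstrap replicates:

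1. Incremental cost and incremental QALYs, each with a 95% interval.
2. Incremental net monetary benefit with its bootstrap 95% interval, over the willingness-to-pay range used for the acceptability curve.
3. The cost-effectiveness plane, beside the acceptability curve already planned.
4. A percentile ICER interval only when the replicates do not materially straddle a zero QALY difference, for example when the 95% interval for incremental QALYs excludes zero; otherwise a Fieller interval, stated as unbounded where it is. Because this rule depends on the data, items 1 to 3 should be reported in every case.

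The net-benefit interval is only as good as the replicates. The SAP should name the analysis population (all randomized or actionable subset), and the resampling should respect site clustering and repeat the cost imputation and any multiple imputation.

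The cost is wording and a different summary of replicates already planned, with no new data. The one downside is that willingness-to-pay values must be named, which the acceptability curve already requires.

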#### **10.7 Interim Analyses**

A single specified interim analysis is planned for each trial. To account for repeated significance testing of the accumulating data, the group sequential method of Lan and DeMets will be used as a guide for

interpreting this interim analysis. Monitoring boundaries for the primary endpoint will be based on a two-sided symmetric O'Brien-Fleming type spending function with an overall two-sided significance level of  $\alpha=0.05$ . The O'Brien-Fleming approach requires large critical values early in the study but relaxes (i.e., decreases) the critical value as the trial progresses.

#### Acute Pain

The interim analysis of the acute pain primary endpoint will compare SIA scores at 10 days post-surgery among participants with *CYP2D6* IM or PM phenotypes in the Control arm to participants with *CYP2D6* IM or PM phenotypes in the intervention arm.

#### Chronic Pain

The interim analysis of the chronic pain primary endpoint, pain control at 3 months post return of PGx testing result to providers, will be compared between the participants with *CYP2D6* IM or PM phenotypes in the Control arm and the participants with *CYP2D6* IM or PM phenotypes in the intervention arm.

#### Depression

The interim analysis of the depression primary endpoint, depression control at 3 months post return of PGx testing result to providers, will compare the participants with *CYP2D6* PM/UM or *CYP2C19* PM, RM and UM phenotypes in the Control arm to the participants with *CYP2D6* PM/UM or *CYP2C19* PM/RM/UM phenotypes in the intervention arm.

The primary analysis is a modified intent to treat design and the analytical subgroup is defined by the results of the PGx testing. Because the drug metabolizer phenotypes for participants in the Control arm is determined around the time of the 6-month follow up assessments for all trials (Acute Pain, Chronic Pain, and Depression), only participants that have completed their 6-month assessments will be included in the interim analysis. To account for the delays in receiving genetic testing results, the interim analysis will be targeted to occur when approximately 50% of the participants have completed their 6-month assessments. If the interim analysis does not propose stopping for efficacy (p-value  $<0.0003$  and the intervention has the larger reduction in the primary endpoints), then the conditional power to detect a significant result at the end of the trial will be estimated. The conditional power will be presented to the DSMB to facilitate discussion of whether the trial should be stopped for futility.

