### 3. ENDPOINTS

#### 3.1 Primary Endpoint(s)

**Acute pain:** The primary endpoint for the acute pain study is the SIA score, a composite of pain and opioid usage, at 10 days post-surgical procedure. See Appendix A for the SIA score rationale.

**Chronic pain:** The primary endpoint for the chronic pain study is change in composite pain intensity score, assessed using the PROMIS pain intensity survey, from baseline to 3 months post return of genetic testing results to the provider.

**Depression:** The primary endpoint for the depression study is change in depression score, assessed using the PROMIS Emotional Distress - Depression 8b survey (adults) or PROMIS pediatric depressive symptoms (pediatric), from baseline to 3 months post return of genetic testing results to provider.

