### **10.4 Analysis of the Primary Endpoint**

#### Acute Pain

To determine the effect of genotype-guided drug therapy on pain control in acute pain participants, we will conduct a subset analysis comparing SIA scores at 10-days post-surgery in the Intervention group subset with CYP2D6 IM or PM phenotypes to the Control group subset with CYP2D6 IM or PM phenotypes. Participants that have other CYP2D6 phenotypes will not be included. The 10-day post-surgery SIA scores of the Intervention CYP2D6 IM/PM group will be compared to the 10-day post-surgery SIA scores of the Control CYP2D6 IM/PM group using a two-sided two-sample t-test or Mann Whitney test, as appropriate, with a type 1 error of 0.049. This primary analysis will be conducted as a modified intent-to-treat analysis, with participants analyzed and endpoints attributed according to the treatment arm to which the participants were randomized, regardless of subsequent crossover or post-randomization medical care.

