### **10.8 Handling of Missing Data**

For all primary and secondary statistical analyses described above, multiple imputation will be used for all missing values except those due to participant death. To ensure that the missing at random assumption for multiple imputation is valid, we will compare baseline pain or depression scores and other patient characteristics in those lost to follow up to participants retained on their randomization assignment. We will also do sensitivity analyses where we compare results obtained with multiple imputation to those obtained without imputation. Missing values due to death will not be imputed and will therefore not be included in the analyses. For exploratory repeated measures analyses, missing data are easily handled as long as the missing at random assumption is valid. However, the missing at random assumption cannot be tested. Accordingly, for exploratory analyses using repeated measures mixed models, we will also conduct a sensitivity analysis where missing values are imputed using multiple imputation. The results with and without multiple imputation will be compared. More complete details of the handling of missing values under different circumstances will be described in the SAP.

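### The interim look admits only 6-month completers although the endpoint is at day 10 or month 3, so its effect estimate and conditional power come from a selected subset of the final mITT population

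*Combined protocol and SAP*

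**What the plan says.** Section 10.7 plans one interim look per trial. In acute pain, "The interim analysis of the acute pain primary endpoint will compare SIA scores at 10 days post-surgery"; the chronic pain and depression looks use the month-3 endpoint. The inclusion rule closes the section and covers all three trials: "only participants that have completed their 6-month assessments will be included in the interim analysis". The reason given is this: "Because the drug metabolizer phenotypes for participants in the Control arm is determined around the time of the 6-month follow up assessments". On timing, "the interim analysis will be targeted to occur when approximately 50% of the participants have completed their 6-month assessments". The look can stop a trial for efficacy at p<0.0003. If it does not, "The conditional power will be presented to the DSMB to facilitate discussion of whether the trial should be stopped for futility".

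The final analysis is set up differently. Section 10.3 takes randomised participants with an actionable phenotype and sets no 6-month condition. Section 10.4 has "participants analyzed and endpoints attributed according to the treatment arm to which the participants were randomized, regardless of subsequent crossover or post-randomization medical care". Under Section 10.8, "multiple imputation will be used for all missing values except those due to participant death".

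Section 7.5 has control samples processed once the control participant has completed the 6-month assessment. It does not say what happens to the samples of controls who never complete it. Intervention samples are processed without that wait.

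**The concern.** In acute pain the primary endpoint is measured "at 10 days post-surgical procedure", nearly six months before the event that decides who enters the look. In the other two trials the gap is three months. Someone who gave a valid primary score and then missed the 6-month survey is removed by something that happened after randomisation and after the endpoint. The look therefore describes a subset of the population that the final test will use.

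Participants and providers are not blinded (Section 4.2) and the outcomes are self-reported, so responding at month 6 could depend on arm and on how the participant is doing. If it does, the interim contrast is shifted, and conditional power projects a completers' effect onto a final mITT test. Even without bias, observed endpoints go unused at the look.

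**Working it through.** **1. Who is in each analysis**

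| | Interim (10.7) | Final (10.3, 10.4, 10.8) |
|---|---|---|
| Phenotype | actionable | actionable |
| Primary endpoint | day 10 / month 3 | day 10 / month 3 |
| Completed month 6 required | yes, both arms | no |

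The sets differ however Section 7.5 is read. If control non-completers are genotyped later, both arms gain participants at the final analysis. If they are not, the intervention arm still does, because its phenotypes are known early. Imputation under 10.8 cannot restore people whom an inclusion rule has removed.

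**2. The plan's own figures**

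Inputs from Section 10.1 and Table 9: two-sided alpha 0.049, 90% power, two-sample t-test. The noncentral t gives:
- acute pain, effect 0.375, 152 per arm: 90.1%
- chronic pain, effect 0.40, 134 per arm: 90.2%
- depression, effect 0.28, 271 per arm: 90.1%

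The plan's sizes reproduce.

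**3. Bias formula**

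Let a share g of one arm have an observed endpoint but no 6-month assessment, and let D (in SD) be the excluded mean minus the retained mean. The full-arm mean equals the retained mean + gD, so dropping these people shifts that arm by gD. The contrast shifts by the difference between the arms' gD values, and by zero when these are equal.

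The documents give neither g nor D. Section 10.1 gives 10% total drop-out, which includes losses before the endpoint, so 10% is used as an upper value. The assumed range is g = 2% to 10% and D = 0.25 to 0.5, in one arm only.

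At g = 10% and D = 0.5 the shift is 0.10 × 0.5 = 0.05 SD. As a share of the planned effect this is 0.05/0.375 = 13% (acute), 0.05/0.40 = 12.5% (chronic) and 0.05/0.28 = 18% (depression).

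**4. Conditional power under the current trend**

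Assume information fraction t = 0.5 and an observed effect of half the planned one. With z = d√(nt/2) and critical value 1.969 (alpha 0.049), CP = Φ[(z/√t − 1.969)/√(1−t)].

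Acute pain, no bias: z = 0.1875 × √38 = 1.156, so CP = Φ[(1.635 − 1.969)/0.707] = 31.8%.

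| Assumption (shift) | Acute | Chronic | Depression |
|---|---|---|---|
| none | 31.8% | 32.0% | 31.6% |
| g 2%, D 0.25 (±0.005) | 29.7 / 34.1% | 29.9 / 34.1% | 28.7 / 34.6% |
| g 5%, D 0.25 (±0.0125) | 26.6 / 37.5% | 27.0 / 37.3% | 24.7 / 39.2% |
| g 10%, D 0.5 (±0.05) | 13.8 / 55.7% | 14.7 / 54.4% | 9.6 / 63.4% |

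Section 10.7 does not say which effect conditional power will assume. If the planned effect is assumed for the remaining data, the extreme row moves it from 75% to 65% or 84% (acute) and from 75% to 60% or 86% (depression).

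**5. Efficacy boundary**

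Two-sided p = 0.0003 is z = 3.615, a one-sided null crossing probability of 0.00015. The extreme shift adds 0.05 × √38 = 0.308 (acute) or 0.05 × √67.75 = 0.412 (depression) to z. The crossing probability becomes about 0.0005 or 0.0007.

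**6. Information left out**

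With half the planned mITT set at the look (152, 134 and 271 in total), g = 2% to 10% removes about 3 to 15, 3 to 13 and 5 to 27 participants. At g = 10% the power to cross p<0.0003 under the planned effect falls from 9.6% to 7.8% (acute), 9.7% to 7.8% (chronic) and 9.5% to 7.7% (depression).

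**The case against.** The rule can be read as a data-maturity cut. It is introduced by the delay in control genotyping, and *completed* may loosely mean *reached month 6*. On that reading the defect is one of wording only. This may be what was intended, but Section 7.5 also ties control genotyping to completing the assessment, which supports the literal reading.

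The rule also follows from Section 7.5: a control whose sample is unprocessed cannot be placed in the actionable subgroup, and applying one rule to both arms keeps selection symmetric. That stands. Relaxing the rule in the intervention arm alone would create an imbalance, so any change must include 7.5.

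A reader might infer that the look is biased, or biased by some 10% or more. The documents do not support that. They give no post-endpoint loss rate, no outcome difference and no evidence that loss differs by arm. Reading the 10% drop-out as loss after the endpoint overstates it, and so does assuming that the excluded participants show no treatment effect.

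A reader might also infer a material threat to the efficacy stop or the final result. The threshold is too strict for the first, and the final set has no completion condition, so the omitted endpoints return there.

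Futility has no fixed cut-off; conditional power only informs a discussion. Separate trial SAPs and a DSMB SAP are promised, and 10.8 arguably covers the interim as well. These points limit the consequence, but the protocol's explicit inclusion rule remains.

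**Conclusion.** The point holds as a mismatch of populations: the look selects on a post-randomisation, post-endpoint event that the final mITT analysis ignores, and the stated reason supports waiting for month 6 rather than requiring the survey. Bias is possible but not demonstrated. Its size rests on assumed values of g and D with loss concentrated in one arm, and ranges from 2 to 3 points of current-trend conditional power to a swing large enough to change a futility discussion in the extreme case. The effect on the efficacy stop is small. The text should be corrected before the look, with futility as the main reason.

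**What to change.** In Section 10.7, define the interim set in both arms as all randomised participants with an actionable phenotype whose 6-month date plus window (14 days in Table 8) has passed at the data cut, whether or not the 6-month survey was completed. Use observed day-10 or month-3 endpoints and handle missing ones as in Section 10.8. Time the look at about 50% of the target having passed that date.

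Amend Section 7.5 to match: stored control samples are processed once the 6-month window has closed, even if the assessment was not completed. Do not relax the rule in the intervention arm alone.

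The cost is wording in 7.5, 10.7 and the DSMB SAP, timely genotyping of control samples already in storage, and slightly more interim analysis work. No extra participants or visits are needed.
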